#### **15.4. Statistical Analysis of Safety Data**

Descriptive statistics will be calculated on the safety parameters using the Safety Population and using actual treatment received. The proportion of subjects with treatment-emergent adverse events will be tabulated and presented by treatment and Medical Dictionary for Regulatory Activities (MedDRA) System Organ Class. Vital signs, LSR scores and clinically relevant abnormal laboratory results will also be tabulated and presented by study medication. No inferential testing will be performed.

Safety summaries by study medication group will include listings by study medication of adverse events incidences within each MedDRA System Organ Class, and changes from pre-application values in vital signs. Adverse event summaries will be presented by study medication showing the proportion of subjects experiencing adverse events, both overall and by MedDRA System Organ Class. The version of MedDRA to be used for the analysis of this study will be specified in the Statistical Analysis Plan.

#### **15.5. Interim Analysis**

No interim analyses are planned for this study.

## **16. QUALITY CONTROL AND QUALITY ASSURANCE**

### **16.1. Protocol Amendments**

No changes from the final approved (signed) protocol will be initiated without the prior written approval or favorable opinion of a written amendment by the IRB/EC, except when necessary to eliminate immediate safety concerns to the study subjects or when the change involves only logistics or administration. The principal investigator and the sponsor will sign the protocol amendment.

### **16.2. Protocol Violations**

A **protocol violation** is defined as any divergence from the protocol-specific inclusion/exclusion criteria, subject is administered a prohibited medication, and/or GCP guidelines. Protocol violations will be identified and recorded, by study center personnel, on the CRF.

As a matter of policy, sponsor/CRO will not grant **exceptions** to protocol-specific entry criteria to allow patients to enter a study. If under extraordinary circumstances such action is considered ethically, medically, and scientifically justified for a particular patient, prior approval from sponsor/CRO and the responsible IRB/IEC, in accordance with the Sponsor/CROs Standard Operating Procedure (SOP), is required before the patient will be allowed to enter the study. If investigative center personnel learn that a patient who did not meet protocol eligibility criteria was entered in a study (a protocol violation), they must immediately inform sponsor/CRO. Such subjects will be discontinued from the study, except in a rare instance following review and written approval by sponsor/CRO and the responsible IRB/IEC, according to the applicable SOP.

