#### **8.4. Withdrawal Procedures**

If a subject withdraws from the study prior to Visit 13, the reason for and the date of withdrawal from the study must be recorded on the eCRF. If the reason for withdrawal is an adverse event or a clinically significant abnormal laboratory test result, monitoring of the subject will continue until the event has resolved or stabilized, until the patient is referred to the care of a local health care professional, or until a determination of a cause unrelated to the study drug or study procedure is made.

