**Table 2: Study Procedures**

Visit	V1 Screening	V2	V3	V4	V5	V6	V7	V8	V9	V10	V11	V12	V13
Treatment Day	-13 to 0	1	8	15	22	29	36	43	50	60	78	106	137
Treatment Window	N/A	N/A	±1 day	+4 days	±7 days	±7 days	+7 days						
Study Procedures													
Informed Consent	▲												
Inclusion Criteria/Exclusion Criteria	▲	▲ 											
Subject Identifier	▲ 												
Medical history/demographics	▲												
Fitzpatrick Skin Type Assessment	▲ 												
Vital Signs	▲ 								▲				▲
Prior Medications/Therapies	▲ 												
Clinical Chemistry and CBC 	▲												▲
Common Wart Identification 	▲												
Physician's Wart Assessment 	▲	▲	▲	▲	▲	▲	▲	▲	▲	▲	▲	▲	▲

Visit	V1 Screening	V2	V3	V4	V5	V6	V7	V8	V9	V10	V11	V12	V13
Treatment Day	-13 to 0	1	8	15	22	29	36	43	50	60	78	106	137
Treatment Window	N/A	N/A	±1 day	±1 day	±1 day	±1 day	±1 day	±1 day	±1 day	+4 days	±7 days	±7 days	+7 days
Common Wart Dimensions 	▲	▲	▲	▲	▲	▲	▲	▲	▲	▲	▲	▲	▲
Standardized Photography 	▲	▲ 		▲		▲			▲	▲	▲	▲	▲
Subject Randomization		▲ 											
Local Skin Reactions		▲ 	▲ 	▲ 	▲ 	▲ 	▲ 	▲ 	▲	▲	▲	▲	▲
Study Medication Application 		▲	▲	▲	▲	▲	▲	▲	▲				
Study Medication Application at Home 			A-101 Study Medication will be applied at home on Days 4, 11, 18, 25, 32, 39, 46, 53. A window of +1 day is allowed.										
Subject Instructions	▲	▲	▲	▲	▲	▲	▲	▲	▲	▲	▲	▲	
Concomitant therapies 		▲	▲	▲	▲	▲	▲	▲	▲	▲	▲	▲	
Adverse Events 		▲	▲	▲	▲	▲	▲	▲	▲	▲	▲		

Subject inclusion/exclusion criteria will be re-assessed prior to randomization during Visit 2.

Investigational sites will assign a unique five-digit subject identifier to each subject at Visit 1. This subject identifier will be used in all study documentation for the duration of the study.

Each subject’s skin must be assessed during Visit 1 using the Fitzpatrick Skin Type Assessment.

Aclaris Therapeutics, Inc.

Protocol Number: A-101-WART-301

Amendment 3: Version 5 14 February 2019

Vital signs [including temperature, pulse, respiratory rate, blood pressure, height and weight (Visit 1 only)] will be measured by a qualified staff member at Visit 1, Visit 9 and Visit 13.

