### 12.3. Physician's Wart Assessment (PWA)

The Physician's Wart Assessment (PWA) is the Investigator's assessment of the severity of each identified common wart at a particular time point. The Investigator should NOT refer to any other assessments to assist with this evaluation. This evaluation IS NOT a comparison with the PWA performed at any other visit.

At every study visit, the Investigator will assess each identified common wart and report the one integer that best describes the common wart severity using the following scale. At any visit where a study medication treatment is performed, the PWA must be completed prior to the treatment visit.

Physician's Wart Assessment	
Grade	Descriptor
0	Clear: No visible wart. No further treatment is indicated
1	Near Clear: a visible wart that is less than 3 mm in maximal diameter (or length)
2	A visible wart $\geq$ 3 mm and $<$ 6 mm in maximal diameter (or length)
3	A visible wart $\geq$ 6 mm in maximal diameter (or length)

The physician is encouraged to use a ruler or caliper and to feel the wart or skin area to help his/her assessment.

At Visit 1 for the subject to be enrolled and at Visit 2 for the subject to be randomized each identified wart must have a PWA grade  $\geq$  2.

At Visits 3-9, identified common warts must have a PWA  $>$  0 to be retreated. If the Investigator cannot assess the PWA for a common wart (e.g., the common wart cannot be visualized because of an LSR such as edema, scabbing, etc.) she/he must report the reason in the subject's CRFs. The identified common wart must not be retreated at that visit, and the subject should be seen at the next scheduled visit. All at home treatment visits will be based on the PWA score during the in-office visit.

Refer to [Appendix 2](#) for the PWA Site Manual.

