### **15.2. Analysis of Populations**

The populations used for analyses will be defined as follows:

- Intent-to-Treat Population (ITT): The ITT population includes all randomized subjects.
- Per-Protocol Population (PP): The PP Population includes all subjects who received at least one application of study medication and have no major protocol violations.
- Safety Population: The Safety population includes all subjects who received at least one application of study medication.

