### **15.3. Statistical Analysis of Efficacy**

The ITT population will be used for primary and secondary efficacy analyses and summaries. The ITT population is defined as all subjects randomized to the study and analyzed as randomized. The Per-Protocol (PP) population will be used for sensitivity analyses for the primary efficacy analysis and all secondary efficacy analyses included in the hierarchical testing procedure. Details on all analyses discussed below will be provided in the study Statistical Analysis Plan (SAP).

The primary efficacy analysis will be a treatment comparison of A-101 45% compared to Vehicle at Visit 10 (Day 60). It will be based on the proportion of subjects who achieve complete clearance (PWA=0) of all identified common warts. A Cochran Mantel Haenszel

(CMH) test stratified by the baseline number of treated warts will be used to perform the primary efficacy comparison between treatment groups, with 2-tail alpha set at 0.05. The analysis will be based on the ITT population. Any identified common wart for a randomized subject that has missing data at the endpoint visit will be treated as not Clear for the purpose of the primary efficacy analysis.

The first sensitivity analysis for the primary endpoint will be an analysis based upon the PP population. This analysis will use the same CMH model described for the primary analysis. A second sensitivity analysis will be conducted for the primary endpoint using the same CMH model for the ITT population that includes the imputation of missing PWA data using a fully conditionally specified (FCS) regression-based Multiple Imputation (MI) procedure. To assess the impact of missing data imputation on the primary analysis results a tipping point analysis will be conducted. This analysis will shift the treatment coefficient in the regression model used in the MI procedure to impose a worse mean maximum PWA for the A-101 45% arm and a better mean maximum PWA for the vehicle arm. Details of this tipping point analysis will be specified in the SAP. In addition, a model similar to the primary analysis model but stratified instead by Study Center will be performed as a sensitivity analysis including a Breslow-Day test to evaluate heterogeneity across sites.

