Four secondary efficacy analyses will be performed and tested in a hierarchical Fixed-Sequence step-down method to control alpha among secondary efficacy variables. The predefined order of the tests is specified to be the order of these analyses as presented below. All analyses will be conducted at the same alpha level (2-tail alpha = 0.05). The results of the second analysis will only be reported if the first analysis reaches statistical significance at alpha = 0.05. The results of the third analysis will only be reported if the first and second analyses reach statistical significance, each at alpha = 0.05. The results of the fourth analysis will only be reported if the first, second and third analyses reach statistical significance, each at alpha = 0.05. Each of the analyses will focus on the outcome of identified common warts at specified time points.

The first secondary analysis will evaluate the effectiveness of A-101 45% compared to Vehicle at Visit 13 (Day 137). It will be based on the proportion of subjects who achieve complete clearance (PWA=0) of all identified common warts. A Cochran Mantel Haenszel (CMH) test identical to the primary efficacy analysis model and stratified by the number of treated warts at baseline will be used to perform the comparison between treatment groups, with 2-tail alpha set at 0.05. Any randomized subject with missing data at the Day 137 visit will be treated as not Clear for the purpose of this secondary efficacy analysis. Sensitivity analyses specified for the primary efficacy analysis will also be performed for this efficacy time point, including missing data imputation impact analyses, the tipping point analysis, and the site heterogeneity analysis.

The second secondary efficacy analysis will be based on a comparison between A-101 45% and Vehicle of the mean per-subject percent of treated warts that are Clear (PWA=0) at Visit 13 (Day 137), using an analysis of variance (ANOVA) model with 2-tail alpha set at 0.05.

The third secondary efficacy analysis will be a comparison between A-101 45% and Vehicle of the proportion of subjects with a single wart at baseline, whose wart is Clear (PWA=0) at Visit 10, using a CMH test stratified by investigator site, with 2-tail alpha set at 0.05.

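### Section 16.2 takes randomised subjects later found ineligible out of the study, so endpoint PWAs that could be observed are scored not Clear in the ITT analysis (small effect, cheap to avoid)

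*Protocol*

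**What the plan says.** **Conduct.** Protocol section 16.2 deals with subjects found after entry not to have met the eligibility criteria: "Such subjects will be discontinued from the study, except in a rare instance following review and written approval by sponsor/CRO", with approval from the IRB/IEC needed as well. Discontinuation is the default, and it is from the study.

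**After leaving.** Section 8.4 requires that "the reason for and the date of withdrawal from the study must be recorded on the eCRF". If the cause is an adverse event or a clinically significant laboratory result, it adds monitoring of that event. It asks for no PWA. Table 2 has columns for Visits 1 to 13 and none for early termination.

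**Analysis.** Section 15.2: "The ITT population includes all randomized subjects". Section 15.3 on the primary endpoint: "Any identified common wart for a randomized subject that has missing data at the endpoint visit will be treated as not Clear". Section 15.3 on the first secondary endpoint: "Any randomized subject with missing data at the Day 137 visit will be treated as not Clear".

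**Per-protocol (PP) population.** Section 15.2: "The PP Population includes all subjects who received at least one application of study medication and have no major protocol violations".

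**Scheduled assessment.** Section 12.3: "At every study visit, the Investigator will assess each identified common wart".

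**The concern.** Each rule is ordinary by itself; the difficulty lies in the combination. A subject is randomised, is later found ineligible, is taken out of the study, stays in the ITT denominator and is scored as a treatment failure. The failure is produced by the conduct rule and is not something anyone observed. The visits at which the wart would have been graded are already in the schedule.

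The protocol itself fixes both the removal and the scoring rule, so this is not a detail left to the SAP. An analysis plan can model outcomes that were never recorded, but it cannot recover them. At stake are some avoidable missing data in the primary and first secondary analyses, and a slight dilution of the treatment difference.

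**Working it through.** **Step 1: which subjects are affected.**

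| Situation | Day 60 (Visit 10, primary) | Day 137 (Visit 13, first secondary) |
|---|---|---|
| Removed under 16.2 before Visit 10 | missing, scored not Clear | missing, scored not Clear |
| Removed after Visit 10 and before Visit 13 | observed PWA is used | missing, scored not Clear |
| Stops study medication but stays in the study | observed PWA is used | observed PWA is used |
| Remains under the approved exception | observed PWA is used | observed PWA is used |

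Only the first two rows lose outcomes.

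**Step 2: inputs for the size.**

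- From section 15.1: 250 subjects per group, and a responder difference of at least 11 points. From section 15.3: two-sided alpha of 0.05.
- Not given in the protocol, so assumed: the vehicle subject-level responder rate pV (5, 7 and 9%) and the share d removed before the endpoint visit (1, 2 and 5%, which is 5, 10 and 25 of 500 subjects).
- Active rate pA = pV + 0.11. A removed subject counts as not Clear, so each rate is multiplied by (1 − d).

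**Step 3: formulas.**

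Difference after removal = 0.11 × (1 − d). This gives 10.89, 10.78 and 10.45 points for d = 1, 2 and 5%.

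Power = Φ{[Δ − 1.96·√(2·p̄(1 − p̄)/n)] / √([pA(1 − pA) + pV(1 − pV)]/n)}, where n = 250, Δ = pA − pV and p̄ is the mean of the two rates. This is an unstratified approximation to the planned CMH test.

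**Step 4: the plan's own figure.** Section 15.1 states more than 90% power, and 97% by simulation. Neither can be reproduced exactly, because the subject-level responder rates and the dropout rate are not given. The first column below (no removal) is consistent with both.

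**Step 5: power (%) with equal removal in both arms.**

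| Assumed vehicle rate | d = 0 | d = 1% | d = 2% | d = 5% |
|---|---|---|---|---|
| 5% | 98.15 | 98.04 | 97.93 | 97.55 |
| 7% | 96.28 | 96.09 | 95.90 | 95.29 |
| 9% | 93.97 | 93.71 | 93.45 | 92.60 |

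Worked example (vehicle 9%, d = 5%): pA = 0.20 × 0.95 = 0.190, pV = 0.09 × 0.95 = 0.0855, Δ = 0.1045, p̄ = 0.13775. The two standard errors are 0.0308 and 0.0305, so z = (0.1045 − 1.96 × 0.0308)/0.0305 ≈ 1.45 and power is 92.6%.

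The smallest loss is 98.15 − 98.04 = 0.11 points and the largest is 93.97 − 92.60 = 1.37 points.

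**The case against.** **The protocol does not contradict itself.** A removed subject is still analysed as randomised under a pre-specified rule. Multiple imputation and tipping-point analyses are planned for Day 60 and again for Day 137, and section 15.1 says anticipated dropout is allowed for. All of this stands, which is why the point is a design improvement and not an error. But the sensitivity analyses model the missing outcomes, and a sample-size allowance protects power; neither supplies the outcome.

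**Few subjects will be affected.** Table 2 says: "Subject inclusion/exclusion criteria will be re-assessed prior to randomization during Visit 2". Section 16.2 also has an exception route. This stands too, and the point claims no more than a small effect.

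**The absence of PWA after leaving is inferred from silence.** Section 8.4 does not forbid a last assessment, and the contents of the termination page named in section 14.2.3 are not shown. That is fair. Even so, an assessment at exit would not be the Visit 10 or Visit 13 outcome.

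**Entry criteria also protect subjects, and 16.2 may serve that purpose.** This stands, and it limits the fix: the sentence in 16.2 may be what ends study medication for these subjects, so a change to follow-up must not alter that.

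**Stronger readings that a reader might infer.**

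- *That removal biases the comparison or takes power below 90%.* With 5% lost in the active arm only, at a vehicle rate of 9%, power would be 89.9%. With 5% lost in the vehicle arm only, it would be 95.8%. The documents show neither pattern, and ineligibility at entry precedes randomisation, so no difference between arms is expected. A vehicle rate of 12% would start at 90.2% and fall to 89.8% with 1% equal removal, but the protocol gives no such rate; its only vehicle figure is 9% per wart.
- *That every removed subject becomes a failure at both time points.* This depends on timing, as Step 1 shows.
- *That sections 8.3 and 14.2.3 also order an end to follow-up.* Section 8.3 is headed as removal from study therapy and turns only conditionally to withdrawal from the study. Section 14.2.3 pairs withdrawal from study drug with a termination page. Both are ambiguous and neither clearly ends PWA visits.

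**Conclusion.** The point holds as a modest one. By default, section 16.2 ends study participation for randomised subjects found ineligible, and nothing asks for their PWA afterwards. Section 15 then scores the missing outcome as not Clear: at Day 60 if removal precedes Visit 10, and at Day 137 if it precedes Visit 13.

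Under equal removal of 1 to 5% before the endpoint and vehicle responder rates of 5 to 9%, the cost is 0.11 to 0.55 points of treatment difference and about 0.1 to 1.4 points of power, which stays at 92.6% or more. Those rates are assumptions, because the protocol states neither. The reason to act is that the missing data are avoidable; the trial's power is not under threat.

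**What to change.** Amend section 16.2 so that a randomised subject found ineligible is asked to continue the scheduled PWA visits through Visit 13 unless consent is withdrawn. Such a subject stays in ITT with observed outcomes, and the violation is handled through the PP population, which section 15.2 already provides for.

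Leave unchanged whatever the protocol requires about study medication for these subjects; no treatment or stopping rule is proposed here. Reconcile sections 8.3, 8.4 and 14.2.3 with 16.2 so that ending study medication and leaving the study are stated as separate events.

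The cost is protocol wording plus continued attendance, at visits already in the schedule, for a few subjects.

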### **16.3. Training**

For each investigational center, there will be an initiation visit prior to enrolling any study subjects.

It is strongly recommended that all investigators, other evaluators, study nurses, study coordinators or other applicable personnel attend this visit. During this visit, participants will be trained to the protocol, study specific procedures, and the CRFs. Those unable to attend the initiation visit must receive on-site training from an appropriately trained individual prior to participating in any of the procedures and evaluations in this study.

Clinical Research Associates (CRAs) and other applicable personnel will be trained prior to study initiation to familiarize CRAs with the disease, the Standard Operating Procedures (SOPs), the protocol and other study specific items. Team organization, communication and operational issues will also be discussed.

Aclaris Therapeutics, Inc. will provide an investigational center file to each center.

### **16.4. Monitoring**

The conduct of the study will be closely monitored by the Aclaris Therapeutics, Inc. study monitor /CRO to verify adherence to ICH Good Clinical Practice (GCP) guidelines, applicable SOPs, the protocol, other written instructions and regulatory guidelines.

The investigator will allow the Aclaris Therapeutics, Inc. representatives designee and/or and any regulatory agency to have direct access to all study records, CRFs, corresponding subject medical records, study medication dispensing records and study medication storage area, and any other documents considered source documentation. The investigator also agrees to assist the representative, if required.

## **16.5. Data Management**

Data will be collected using CRFs that are specifically designed for this study. The data collected on the CRFs will be captured in a clinical data management system (CDMS) that meets the technical requirements described in US 21 Code of Federal Regulations (CFR) Part 11. The CDMS will be fully validated to ensure that it meets the scientific, regulatory, and logistical requirements of the study before it is used to capture data from this study. Before using the CDMS, all users will receive training on the system and study specific training. After they are trained, users will be provided with individual system access rights.

The handling of data, including data quality assurance, will comply with regulatory guidelines, including ICH and GCP, and the sponsor/CRO SOPs and working instructions. Data management and control processes specific to this study will be described in a data management plan. At the end of the study, the database will be locked and the data will be released for reporting and statistical analysis.

## **16.6. Quality Assurance**

The study is conducted under the sponsorship of Aclaris Therapeutics, Inc. in compliance with the applicable regulatory requirements as well as applicable ICH guidelines, Helsinki Declaration, and in respect of the Aclaris Therapeutics, Inc. and/or sub-contractor SOPs for study conduct and monitoring.

Audits may be carried out by the Aclaris Therapeutics, Inc. or Aclaris Therapeutics, Inc.'s representatives and inspections may be performed by regulatory authorities or IRB/ECs before, during or after the study. The investigator will provide the auditing/inspecting group direct access to all study records (*e.g.*, CRFs, subject medical records, study medication dispensing records) and the investigational center study facilities. The investigator and study staff will be available and will assist the auditing/inspecting groups as appropriate.

